- ECMO delivery is veno-venous with internal jugular catheter.

Exclusion Criteria

- Femoral catheter of any kind present.
- Veno-arterial ECMO setup.
- Sedation such that self-consent is not attainable.
- Medical instability, as determined by primary critical care physician.

Overview of Protocol for Aims 1-3:

Participants in either Group A (closed chain leg exercise group) or B (open chain exercise group) will progress through the established ECMO protocol led by their physical therapist. Participating therapists have extensive experience in working with patients on the Moveo who are in the ICU. Subjects will be assisted in the supine position from their bed to the Moveo device via a lateral transfer across a slide board to facilitate ease of movement.

Those in Group A will participate in leg exercise on the Moveo during item 4d of the ECMO protocol, whereby those in Group B will complete standard exercise as listed in item 4d. Group A participants will use the Moveo until subjective report of leg fatigue. Participants will self-select the pace of their leg exercise and the primary therapist will determine guidelines for percent of body weight lifted in accordance with standard practice physical therapy. Subjects will complete 1-4 sets of up to 25 reps of the squat exercise with 2 minutes of rest between each set. Subjects will receive physical therapy 5 days/week regardless of randomization into Group A or Group B.

Data Collection for Aims 1-3: Data will be collected on Day 0 (physical therapy evaluation day), Day 5, Day 10, Day 15, Day 20, Day 30, Day 45 (if applicable), and Day of discharge. Data collected will be categorized as specific to Aim 1 (time from initial physical therapy evaluation to initial ambulation), Aim 2 (functional outcomes) and Aim 3 (hospital outcomes). Recording of physiological data including heart rate (HR), blood pressure (BP), oxygen saturation (O2), and respiratory rate (RR) will be completed by trained physical therapists involved in the protocol at the onset of, and 1-minute post-conclusion of each therapy session. Therapy sessions are to be delivered at a frequency of five sessions per week.

- Functional Outcomes

- Leg strength as assessed by primary therapist via manual muscle test, using the Medical Research Council Sum Score (MRC Score)
- Grip strength, as assessed by hand dynamometer, completed by primary therapist

- 30-second sit to stand, completed by primary therapist

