 - Richmond Agitation and Sedation Scale (RASS), as completed in medical record by primary nurse
 - Functional Status Score for the Intensive Care Unit (FSS-ICU)
- Hospital Outcomes (data extraction from medical record)
 - Hospital days
 - Intensive care unit days
 - Days on ECMO
 - Days on mechanical ventilation
 - Length of time from physical therapy evaluation to initial ambulation
 - Discharge disposition- assigned a number for statistical analysis
 - Home (1)
 - Home with assistance (2)
 - Home with home therapy (3)
 - Home with outpatient therapy (4)
 - Transitional Care Unit (5)
 - Acute Inpatient Rehabilitation (6)
 - Long-term acute care hospital (7)
 - Long-term care setting (8)
 - Transfer to outside hospital (9)
- Physiological Monitoring: Monitoring physical therapists have extensive experience in mobilizing patients in the ICU, including those with arterial lines and on ventilation, as is standard practice for ICU therapy.
 - Respiratory rate (RR) via Drager Ventilators
 - Evita Series or Infinity Series
 - Oxygen (SpO2) and heart rate (HR)
 - Spacelabs Ultraview SL2700 (regular monitor)
 - Spacelabs Ultraview SL (portable monitor)
 - Blood Pressure (BP) via manual cuff or arterial line
 - Spacelabs Ultraview SL2700 or SL

Statistical Considerations

Physiological data (HR, BP, O2, RR) will be recorded throughout the study and analyzed between Groups A and B. Functional and Hospital outcomes will be analyzed to compare group differences at each of the data collection days (0, 5, 10, 15, 20, 30, 45, day of discharge).

Data will be analyzed at the University of Minnesota using the Statistical Package for Social Sciences (SPSS) software program. Test for normality will be completed via a paired t-test for parametric data and via Wilcoxon Rank Sum Test for non-parametric data.

Aim 1: Leg exercise on the Moveo will decrease time to initial ambulation.

- A paired t-test will be used to evaluate time to ambulation in Group A as compared to Group B.

Aim 2: Leg exercise on the Moveo will improve functional outcomes.

- There are 2 primary factors to assess, Group A and B, as well as the impact across time. To assess both factors, repeated measures ANOVA will be used.

Aim 3: Leg exercise on the Moveo will improve hospital outcomes.

- All hospital outcomes, except for discharge disposition, can be assessed between Group A and Group B by a paired t-test.
- Discharge disposition, categorical data, will be analyzed via Chi-Square test.

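### Aim 2 assessments are tied to fixed days with no window while therapy runs five days a week, and the planned repeated measures ANOVA handles the resulting gaps poorly

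*Combined protocol and SAP*

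**What the plan says.** All the places below are in the combined protocol and SAP.

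- **Assessment days.** Under Data Collection for Aims 1-3 the plan states: "Data will be collected on Day 0 (physical therapy evaluation day), Day 5, Day 10, Day 15, Day 20, Day 30". To these it adds Day 45 where that applies, and the day of discharge. No window is given around any of these days.
- **Therapy frequency** (Overview of Protocol for Aims 1-3): "Subjects will receive physical therapy 5 days/week regardless of randomization into Group A or Group B". The data collection paragraph repeats it: "Therapy sessions are to be delivered at a frequency of five sessions per week". Neither statement names the days.
- **Assessor** (Functional Outcomes). The first measure listed is "Leg strength as assessed by primary therapist via manual muscle test". The second is given as "Grip strength, as assessed by hand dynamometer, completed by primary therapist", and the third as "30-second sit to stand, completed by primary therapist". RASS comes from the nursing entry in the medical record, and no assessor is named for FSS-ICU.
- **Occasion of measurement** (section 2.2): individual data are gathered within scheduled physical therapy sessions.
- **Analysis** (Statistical Considerations): groups are compared at each nominal day. For Aim 2, with group and time as factors, "To assess both factors, repeated measures ANOVA will be used".
- **Length of follow-up** (Research Design & Methods): patients take part for as long as they are on ECMO and in hospital. No minimum stay is set.

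**The concern.** Three functional outcomes depend on the therapist being with the patient in a session on a particular numbered day. A five-day therapy week leaves two days without a session, and most of the intervals between assessments are not whole weeks, so the assessment weekday shifts through the stay. The plan does not say what happens when a numbered day has no session. The assessment could be moved, missed, or done outside a session.

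Each outcome has a cost in the Aim 2 analysis. A missed value makes the patient incomplete, and repeated measures ANOVA in its standard form keeps only patients with every time point. A moved value is analysed as if taken on the nominal day unless the true date is recorded. With a target of 10 patients per group, there is little room for avoidable loss of either kind.

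**Working it through.** The plan gives no figure for assessments on days without therapy, so there is none to reproduce. The check is a calendar count.

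**Inputs from the plan.** Assessment days 5, 10, 15, 20, 30 and 45; five therapy days a week; Day 0 is the physical therapy evaluation day. The discharge visit is left out of the count because its day is not fixed.

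**Assumptions, not in the plan.** Therapy is Monday to Friday, Day 0 is a weekday with starts spread evenly, and numbered days are calendar days.

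**Formula.** Number Monday to Sunday as 0 to 6. Then assessment weekday = (Day 0 weekday + day number) mod 7, and a result of 5 or 6 is a day without therapy. The day numbers 5, 10, 15, 20, 30, 45 leave remainders 5, 3, 1, 6, 2, 3.

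| Day 0 | Assessments on a weekend | Count |
|---|---|---|
| Monday | Days 5, 20 | 2 |
| Tuesday | Day 5 | 1 |
| Wednesday | Days 10, 45 | 2 |
| Thursday | Days 10, 30, 45 | 3 |
| Friday | Days 15, 30 | 2 |

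Total: 2 + 1 + 2 + 3 + 2 = 10 of 5 × 6 = 30, or 33.3%. By nominal day, 2 of 5 starts (40%) are affected at Days 5, 10, 30 and 45, and 1 of 5 (20%) at Days 15 and 20. At Day 5 with 10 patients per group, that is 0.40 × 10 = 4 expected per group.

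**Shorter stays, same assumptions.**

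| Followed to | Weekend assessments | Start days with none |
|---|---|---|
| Day 5 | 2/5 = 40% | Wednesday, Thursday, Friday |
| Day 10 | 4/10 = 40% | Friday |
| Day 15 | 5/15 = 33.3% | none |
| Day 20 | 6/20 = 30% | none |
| Day 30 | 8/25 = 32% | none |
| Day 45 | 10/30 = 33.3% | none |

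**Varying the assumptions.**

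- *Day 0 on any of seven days, weekends off, stay to Day 45.* A Saturday start adds Day 15 and a Sunday start adds Day 20: 12 of 7 × 6 = 42, or 28.6%. A Sunday start has no affected assessment before Day 20.
- *Any other fixed pair of weekly days off, Day 0 a therapy day.* Through Day 30 the remainders are 5, 3, 1, 6 and 2, which is every non-zero value except 4. Two different days off cannot both be at remainder 4, so at least one assessment is affected. The average to Day 45 is again 33.3%. A non-consecutive pair at remainders 2 and 4 gives none through Day 20.
- *Therapy days chosen week by week.* No calendar week holds more than two scheduled assessment days, so five therapy days can always include them: 0%.

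**Would a ±1 day window suffice?** With weekends off, Saturday is one day from Friday and Sunday one day from Monday, so yes. The numbered days are at least 5 days apart, so their windows (for example Days 4 to 6 and 9 to 11) cannot overlap one another. The discharge visit can fall inside any of them.

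**The case against.** The strongest reply is that the two schedules do not contradict each other. The plan never says Monday to Friday and never says that the days off are fixed, so staff could place the five sessions around the assessments and follow both statements exactly. It also does not say whether Day 5 is a calendar day or the fifth therapy day. All the numbered days are multiples of five, and on a therapy-day count nothing would be displaced. This stands, and it is why the percentages above are conditional. It does not remove the need for a rule, because the plan writes down neither arrangement.

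A second reply is that the effect is small. A shift to the nearest therapy day is one day, therapy frequency is the same in both groups, and only three functional measures are clearly tied to the therapist. The main source of incomplete patients is discharge before the later days, which happens whatever the calendar. All of this stands. The calendar adds an avoidable loss to a larger one, and both point to the same change of analysis.

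A reader might go further and infer that every patient has a displaced assessment, that one third are displaced as a matter of fact, or that no patient could have a complete set. The documents do not support these. A patient discharged by Day 10 can have no affected assessment, the one-third figure needs the assumptions listed, and the plan does not say that an assessment due on a day without therapy is lost.

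**Conclusion.** The point holds in conditional form. With Monday to Friday therapy, weekday evaluations and calendar days, about 30% to 40% of the therapist-done assessments fall on a day without therapy, depending on length of stay (10 of 30 to Day 45). Every patient followed to about Day 15 has at least one, or to Day 20 if Day 0 can be a Sunday. The share is 28.6% if evaluations occur on any day of the week, and 0% if sessions are arranged around assessments or the days are counted in sessions.

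The consequence is timing noise and missing values at nominal days. It falls on both groups alike by design, and no between-group bias is shown. The missing window alone would be a matter of detail. What makes the point worth acting on is that the stated Aim 2 method, in its standard form, discards patients with any gap, in a trial where stays vary and Day 45 applies only to some.

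**What to change.** For Aim 2, replace the repeated measures ANOVA with a linear mixed model that uses all available assessments, with group, time and their interaction, and with time entered as actual days since Day 0. Add to the data collection paragraph:

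- the actual date of each assessment is recorded;
- an assessment may be done on the nearest therapy day within ±1 day of the numbered day;
- an assessment that falls in both a scheduled window and the discharge visit is entered once, at its actual day.

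State also that numbered days are calendar days, if that is what is meant. The therapy schedule is unchanged.

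The cost is a few sentences, one date field, up to one day of variation in timing, and slightly more analysis work. The mixed model keeps patients with partial data, but it does not by itself settle whether discharge is related to values that were never observed. That is a separate missing-data question.

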15.0 Compensation for Research-Related Injury

15.1 Compensation for Research-Related Injury: N/A

15.2 Contract Language: N/A

16.0 Consent Process

16.1 Consent Process (when consent will be obtained): Once subjects are removed from sedation and able to follow 3/3 one-step commands.

- Consent will occur in the hospital room of the subject. There will be no waiting period between initial consent and initiation of study.
- Ongoing verbal consent to activity will be addressed daily, when the therapist approaches a subject for scheduled therapy.
- Consent will be obtained via pre-approved form.

16.2 Non English-Speaking Participants: Any non-English speaking individual who is being treated by a physical therapist and who is undergoing ECMO treatment would be eligible for consent. As advised by IRB, a line on the consent form indicating who facilitated consent in the case of a non-English speaker, has been added.

PROTOCOL TITLE: The Impact of Lower Extremity Weight-Bearing Leg Exercise During the Pre-Ambulation Phase of Individuals Undergoing Extracorporeal Membrane Oxygenation (ECMO)
VERSION DATE: 11/28/16

16.3 Participants Who Are Not Yet Adults (infants, children, teenagers under 18 years of age): N/A

16.4 Cognitively Impaired Adults, or adults with fluctuating or diminished capacity to consent: N/A

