Aim 1: To determine if closed-chain leg exercise decreases the time to initial ambulation. *We hypothesize* that adding leg exercise will decrease time to ambulation.

Aim 2: To determine the impact of closed chain leg exercise on functional ability. *We hypothesize* that adding leg exercise will improve functional outcomes when added to an existing early mobilization program.

Aim 3: To determine the effect of closed chain leg exercise on hospital outcomes. *We hypothesize* that hospital related outcomes will improve when leg exercise is added to an existing early mobilization program.

Research Design & Methods

This initial pilot study will be conducted at the University of Minnesota Medical Center (UMMC), Fairview, and will involve 10 participants in each of the two groups (A and B). To account for attrition, 24 total subjects will be recruited; 12 per group. Approximately 3-5 patients are admitted to UMMC each month who are undergoing ECMO and could be considered for study inclusion. The study will be conducted with a goal endpoint of 1-year. Men and women aged 18-70 years old with refractory respiratory failure who are undergoing ECMO will participate over the duration of their ECMO treatment and hospitalization.

Recruitment and Consent

Standard practice includes a physician order for inpatient physical therapy for all individuals undergoing ECMO, as well as initial medical sedation. Most of those receiving ECMO are at least partially medically sedated at the time of physical therapy initiation. Only physical therapists who are specialty-trained ICU therapists and who are a part of this project will be working with this group of patients.

Any individual who meets inclusion criteria will be considered for participation, pending their ability to follow 3/3 one-step commands, as is outlined in the ECMO Mobility Protocol listed previously. Patients will be able to self-consent once sedation is reduced. After consent, individuals will be placed into either Group A or B and progress through the protocol. Group assignments will be determined based on 24 subjects, with the number 24 put into a random letter sequence generator prior to subject recruitment.

Inclusion Criteria

- Men and women 18-70 years old with refractory respiratory failure undergoing ECMO at the University of Minnesota Medical Center, Fairview.
- Able to follow 3 out of 3 one-step commands via protocol.
- Active Inpatient Physical Therapy Referral.

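### Day 0 leg strength and grip are set for the physical therapy evaluation day, which can precede command-following in an unstated share of participants, yet Day 0 is the first time level of the Aim 2 analysis

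*Combined protocol and SAP*

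**What the plan says.** All references are to the combined protocol and SAP.

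- **Day 0.** Data Collection for Aims 1-3 states: "Data will be collected on Day 0 (physical therapy evaluation day". The same paragraph defines Aim 1 as "time from initial physical therapy evaluation to initial ambulation", so the evaluation meant is the initial one.
- **Sedation at that time.** Recruitment and Consent: "Most of those receiving ECMO are at least partially medically sedated at the time of physical therapy initiation".
- **Entry.** The Inclusion Criteria require "Able to follow 3 out of 3 one-step commands via protocol". The Exclusion Criteria list "Sedation such that self-consent is not attainable". Section 16.1 places consent "Once subjects are removed from sedation and able to follow 3/3 one-step commands". Section 9.1 adds that those consented are already under the care of the physical therapists, and group placement follows consent.
- **Order of mobilization.** In the ECMO Early Mobilization Protocol, following 3/3 commands is step c, after passive range of motion (a) and lift-assisted sitting to promote wakefulness (b).
- **Measures.** Functional Outcomes lists "Leg strength as assessed by primary therapist via manual muscle test, using the Medical Research Council Sum Score (MRC Score") and grip by hand dynamometer.
- **Analysis.** Statistical Considerations compares functional outcomes between groups at every collection day, Day 0 included. For Aim 2, with group and time as factors: "To assess both factors, repeated measures ANOVA will be used".

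No section says how a strength or grip test that cannot be performed is recorded or analysed. None names a baseline other than Day 0, and no missing-data method is given.

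**The concern.** Both tests measure voluntary effort on instruction, and a patient who cannot follow commands cannot give a valid score. The schedule ties the first test to the start of physical therapy, whereas the entry criteria tie command-following to consent, which comes later. Between the two, the protocol itself expects sedation to be reduced.

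A participant not yet following commands on Day 0 has either no value or a low value caused by sedation. In the first case, standard repeated measures ANOVA needs every time level and drops the participant from the analysis. In the second, part of the apparent gain from Day 0 to Day 5 is sedation wearing off. A chance difference between arms in the number sedated at evaluation could then look like a group-by-time effect.

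Strength is the most direct target of a leg-press exercise, and the Project Summary names it as a factor in time to mobilization. With 10 evaluable patients per arm there is little room to lose any.

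**Working it through.** **Sample arithmetic.** The plan gives no power, effect size or SD, so the sample is the only figure to check. Research Design & Methods states 10 per group, with 24 recruited to allow for attrition. The implied attrition is 1 − 20/24 = 16.7%, and 20/(1 − 0.167) = 24. The figures are consistent, and 10 per arm is the evaluable number used below.

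**Sequence in time.**

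1. The initial physical therapy evaluation is Day 0, with strength and grip scheduled. Most ECMO recipients are then at least partially sedated.
2. Mobilization steps a and b follow, before command-following is shown.
3. At step c, 3/3 commands are followed and consent becomes possible.
4. Consent and group placement come next.

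The command-following criterion is met at point 3 or later, whereas the measurement is due at point 1. Meeting it later does not make the earlier value valid. Nothing requires points 1 and 3 to fall on the same day, and nothing prevents it.

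**Patients left with a Day 0 value.** Let *s* be the share of participants untestable on Day 0. The documents do not give it, so the values of *s* are assumptions. The mean number left per arm is 10 × (1 − *s*).

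**Power.** The illustration is a two-sided 5% two-sample t-test for a 1.3 SD difference. Neither the alpha nor the effect is in the documents. With *n* per arm, degrees of freedom are 2*n* − 2 and the noncentrality is 1.3 × √(*n*/2).

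| *s* | mean per arm left | noncentrality | critical t | power |
|---|---|---|---|---|
| 0 | 10 | 1.3 × √5 = 2.91 | 2.10 | 78% |
| 10% | 9 | 1.3 × √4.5 = 2.76 | 2.12 | 74% |
| 25% | 7.5 | 2.43 (n=7) to 2.60 (n=8) | 2.18 to 2.14 | 61% to 68% |
| 40% | 6 | 1.3 × √3 = 2.25 | 2.23 | 53% |
| 50% | 5 | 1.3 × √2.5 = 2.06 | 2.31 | 44% |

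**Precision.** The 95% half-width for a difference in means is t × √(2/*n*) in SD units. It is 2.10 × √0.2 = 0.94 at *n* = 10 and 2.31 × √0.4 = 1.46 at *n* = 5.

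These figures are for a simple two-group contrast, not the group-by-time test, and they take every other visit as complete. They show direction and rough scale only.

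**The case against.** The strongest reply is that the documents do not show how often this happens.

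- The sedation sentence says at least partially sedated, gives no sedation score or percentage, and does not say that such patients cannot follow commands.
- It describes ECMO recipients in general. Participants are a selected group: veno-venous ECMO by internal jugular catheter, 3/3 commands followed, able to self-consent.
- The mobilization steps give an order, not dates, and Day 0 is a whole day. Some participants may reach step c on the day of evaluation.
- Day 45 is collected only if applicable and the discharge day varies, so complete-case ANOVA would lose patients whatever happens on Day 0.

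All of this stands, and it limits the claim. A reader might infer from the sedation sentence that most participants cannot be validly scored on Day 0. The documents do not support that, for the first two reasons. A reader might also infer that untestable patients will be scored 0, but no section says so.

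The reply does not remove the timing fault. The entry criteria apply at consent, not at Day 0, and the protocol expects sedation to fall in between. The Richmond Agitation and Sedation Scale is collected and could document who was testable, but the plan does not use it for that.

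**Conclusion.** The point holds in a limited form. The schedule places effort-dependent leg strength and grip tests on a day that comes before consent and can come before command-following. It then makes that day the first time level of the Aim 2 analysis, with no rule for tests that cannot be scored. This follows from the text without any assumption about numbers.

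The size is unknown because the share affected is not stated. Under the assumed 1.3 SD effect, complete-case analysis and otherwise complete data, even a 40% share would take power from 78% to 53%. A 10% share would cost little by loss of patients alone (74%). The change is worth making before enrolment because it costs little and an invalid baseline cannot be recovered afterwards.

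**What to change.** In Data Collection for Aims 1-3, for leg strength and grip:

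- Take the baseline at the first session in which the patient follows 3/3 commands, after consent and before the group assignment is opened. Use it as the baseline in the Aim 2 analysis.
- Count the follow-up days for these measures from that baseline, or use only the scheduled assessments that fall after it. Otherwise Day 5 or a later visit, still counted from evaluation, could precede the baseline.
- Record an untestable assessment as missing, never as 0.
- Record the number of days from evaluation to baseline.

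Keep the evaluation day as the time origin for Aim 1.

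**Cost.** The change uses an existing milestone, the same assessor and a session that already takes place, and it alters no treatment. It is more than a wording edit, because the follow-up schedule for these two measures has to be re-anchored or restricted. The baseline will also fall at a varying interval after evaluation, which is why that interval should be recorded. Section 16.1 allows no waiting period between consent and study start, so the baseline test has to be written into that step, before the assignment is opened.

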Collecting and analyzing data on weight-bearing lower extremity exercise in this patient population will allow us to obtain important information on ways to address weakness associated with ECMO treatment, particularly in those who are unable to engage in bipedal ambulation.

[figure not shown]
MOVEO XP Mobile Hi-Lo Platform System

Company Website:

<http://www.djoglobal.com/products/charlottesville/moveo-xp>

ECMO Early Mobilization Protocol:

1. **Readiness for Mobility Assessment and Protocol** (Developed by ECMO therapy specialists at the University of Minnesota Medical Center)
 - a. Passive range of motion (PROM) and monitor for appropriateness of entering into the mobility program
 - b. Utilization of lift equipment to sit patient at the edge of the bed or into chair to promote wakefulness, when on minimal amounts or no sedation
 - c. Patient demonstrates the ability to follow 3/3 one-step commands
 - d. Patient tolerates 5 minutes of lower extremity ergometer, or performs ten reps of 3 active ROM of motion exercises involving the lower extremities
 - e. Sit at bedside unsupported for 5 minutes
 - f. Sit->stand and pre-gait activities (weight shifting, walking in place, etc.) directed by therapist
 - g. Bed->chair transfers (stand-pivot or squat-pivot)
 - h. Walking over ground with utilization of the mobility carts

The primary aim of this study is to assess the functional impact of leg exercise during the pre-ambulation phase in patients undergoing ECMO. Outcome measures will be categorized as either functional or hospital based. Hospital measures include: Hospital days, intensive care unit days, days on ECMO, days on mechanical ventilation, length of time from physical therapy evaluation to initial ambulation, and discharge disposition. Functional outcome measures include: Leg strength, grip strength, 30-second sit to stand test, Functional Status Score for the Intensive Care Unit (FSS-ICU), and the Richmond Agitation and Sedation Scale (RASS).

Background & Significance

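### Aim 2 analyses RASS and the 30-second sit to stand as raw values by repeated measures ANOVA, with no direction set for RASS and no score for patients who cannot yet stand, so results for both can mislead.

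*Combined protocol and SAP*

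**What the plan says.** All references are to the Project Proposal part of the combined document.

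- **Hypothesis.** Specific Aims, Aim 2, expects that "adding leg exercise will improve functional outcomes when added to an existing early mobilization program".
- **Outcomes.** There are five functional outcomes: leg strength, grip strength, sit to stand, FSS-ICU and RASS. Two are at issue here: "Richmond Agitation and Sedation Scale (RASS), as completed in medical record by primary nurse" and "30-second sit to stand, completed by primary therapist". No range, target or favourable direction is given for RASS. No score is given for a patient who cannot yet do the sit to stand test.
- **Schedule.** Data Collection for Aims 1-3 sets one list of days for all outcomes: Day 0 (the physical therapy evaluation), 5, 10, 15, 20, 30, 45 if applicable, and discharge.
- **Analysis.** Statistical Considerations, Aim 2, names group and time as the factors and states: "To assess both factors, repeated measures ANOVA will be used". The same section also plans group comparisons at each collection day.
- **Entry.** Inclusion requires "Able to follow 3 out of 3 one-step commands via protocol"; an exclusion is "Sedation such that self-consent is not attainable". Recruitment and Consent says that most ECMO patients are still at least partly sedated when therapy begins, that they consent once sedation is reduced, and that they enter a group after consent.
- **Mobility ladder.** In the ECMO Early Mobilization Protocol, step d is leg exercise, step e is unsupported sitting, and step f is "Sit->stand and pre-gait activities (weight shifting, walking in place, etc.) directed by therapist". The Project Summary places the Moveo at parts C and D; the Overview of Protocol places it at item 4d only. These two passages need reconciling, but both put the Moveo before step f.

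**The concern.** **RASS.** A mean is useful when higher is better, or lower is better, throughout. The name of this scale puts sedation at one end and agitation at the other, so improvement has no fixed sign on the raw score. A group with some sedated and some agitated patients can have the same mean as a calm group, and a more agitated group can look better.

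The baseline adds a second difficulty. Day 0 is the therapy evaluation, which can come before consent and assignment. Part of any rise from Day 0 is then lightening of sedation before assignment. It is common to both groups and says nothing about the exercise, yet it enters the time factor.

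**Sit to stand.** The test is due on days when many patients will not have reached that activity. If those values are blank, a conventional repeated measures ANOVA drops every patient with a gap. A by-day comparison then covers only patients who have already progressed to standing, which is what the Moveo is meant to hasten. If it brings weaker patients to standing sooner, they join Group A with low counts and pull its mean down.

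Two of the five Aim 2 outcomes are affected, with 10 evaluable patients per group.

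**Working it through.** The plan gives no figure for this analysis. Its sample size is internally consistent (2 × 12 = 24; 1 − 20/24 = 16.7% attrition) but has no stated alpha, power, effect or SD. Every distribution below is therefore an assumption. The simulations use 10 per group, two-sided 0.05 and Days 0, 5, 10, 15, 20 and 30.

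**1. RASS by hand.** Take 0 as the calm target (an assumption; the documents give no range).
- Group A all at 0; Group B half at −1 and half at +1. Means: 0 and (−1 + 1)/2 = 0. Difference 0, although only Group A is calm.
- One group all at +1, the other all at 0. Difference 1, which counts as improvement if higher is taken as better.

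**2. RASS by simulation.** The group effect is a t-test on patient means, which is the between-group test of the ANOVA.
- Scatter on both sides of 0, with probabilities for −2 to +2 of 0.02, 0.13, 0.70, 0.13, 0.02 in A and 0.10, 0.25, 0.30, 0.25, 0.10 in B. Both means are 0. Mean distance from 0 is 0.34 in A and 0.90 in B. Power is 4.9% on the raw score (no better than alpha) and 99% on distance from 0. Visits were drawn independently, so 99% is optimistic; the contrast is the point.
- Groups differing only on the sedated side: means −0.11 against −0.38 give 27% power on the raw score; −0.23 against −0.68 give 55%.

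**3. Sit to stand, when values exist.** Assume a median time to step f of 6 to 15 days in B and 4 to 8 days in A. The share not yet at step f, or scoring 0, is:

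| Day | Share |
|---|---|
| 0 | 100% (by construction) |
| 5 | 50-88% |
| 10 | 14-56% |
| 30 | 0-7% |

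- Blanks before step f: 0 of 20 complete cases. This follows from assuming that nobody is at step f on Day 0; a few patients who could stand on Day 0 would leave a few cases.
- Zeros before step f: power 38-84% for the group effect, 33-77% for the slope, and 30-72% for a rank test at Day 30, over the assumed effects. With no true effect the group test rejects about 5% of the time.

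**4. Sit to stand, selection among those able to stand.** Assume latent capacity L ~ N(δ, 1) in A and N(0, 1) in B, standing possible when L > τ, and repetitions = a + b(L − τ) for those who can stand. With x = δ − τ (x = −τ in B):
- share able to stand: P = Φ(x)
- mean over all, with unable = 0: M = aP + b[xΦ(x) + φ(x)]
- mean among those able: M/P

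For δ = 0.5, τ = 0, a = 1, b = 4:
- A: P = 0.691; M = 0.691 + 4(0.5 × 0.691 + 0.352) = 3.483; M/P = 5.037
- B: P = 0.500; M = 0.500 + 4 × 0.399 = 2.096; M/P = 4.192
- Difference over all patients: 3.483 − 2.096 = 1.387
- Difference among those able: 5.037 − 4.192 = 0.845
- Loss: 1 − 0.845/1.387 = 39%

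Sensitivity, with δ from 0.3 to 0.8 and τ of 0 or 0.5:

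| a, b | Loss |
|---|---|
| 1, 4 | 36-40% |
| 0, 4 | 19-29% |
| 1, 1 | 54-60% |

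In SD units the main case is 0.46 against 0.32, a loss of 1 − 0.32/0.46 = about 30%. The direction is the same in every case tried; the size depends on the inputs.

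**The case against.** The tempting stronger reading is that neither outcome can show the hypothesised improvement. The documents do not support it. Patients are followed through hospitalisation, and groups are compared on each collection day, so a floor shared at Day 0 leaves room for a later difference. With zeros scored, the simulated power for sit to stand was 38-84%. Even among those able to stand, the illustrated difference stays positive. Raw RASS also detects a shift confined to the sedated side.

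A reader might also infer that the entry rules hold RASS near its best value throughout. They act at enrolment only: Day 0 can be earlier, when patients are sedated, and nothing restricts sedation later. They also act equally in both groups, so a shared rise from Day 0 affects the time factor and does not bias the group comparison.

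Nor does the plan say that a patient short of step f has a missing value. Step f describes therapist-directed activity and is not a rule for recording the test. If inability is scored 0, the selection problem goes away.

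Finally, the mid-scale RASS target is an inference from the name, exact cancellation is a constructed case, and no single percentage loss can be claimed for this trial. Those objections stand.

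What they leave is a stated analysis of raw values with no direction for RASS, and a sit to stand outcome whose meaning turns on a scoring rule that the plan omits.

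**Conclusion.** The concern holds as one of interpretability and possible bias. For RASS it follows from the stated method and the name of the scale: the group mean has no defined good direction, can hide opposite deviations and can reward agitation. How often that would happen here is unknown. For sit to stand it is conditional: if values before step f are left blank, most or all patients drop out of a complete-case ANOVA, and by-day comparisons are selected on progress after assignment. Under the latent-capacity model above, that selection attenuates a true benefit by between 19% and 60%, depending on the assumed inputs.

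The trial is a small pilot, three other functional outcomes are unaffected by this point, and time to ambulation is handled separately under Aim 1. The correction is still worth making before any outcome data are compared, because a later choice between zero and blank, or of a RASS direction, could change the result.

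**What to change.** - **RASS.** Do not analyse it as a raw mean. Either report it descriptively, as the patient's state at each assessment, or compare the proportion of assessments in a calm/alert range that the investigators define in advance. State that change from Day 0 can include change before assignment.
- **Sit to stand.** Score a patient not yet able to stand as 0 with a 'not yet able' flag, keep the patient in the comparison, and use a rank-based test. The flag should separate inability from a test missed for other reasons.
- **Schedule.** Reconcile the Day 0 start of sit to stand collection with step f. The statistical plan needs only the scoring rule; when the test may be attempted is a clinical matter for the investigators.

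The cost is some protocol and analysis wording and one data field. The drawbacks are many zeros on early days, which carry little information, and the loss of a mean RASS.
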